5.5.7.3. Data Collection for Quantitative Evaluations of Implementation Process

- Edited costs and budget impact analysis section to more clearly and accurately explain our proposed analyses.

Version 2.8 02/22/2023

Abstract

- Updated 'progress to date' section to reflect that recruitment began 4/4/2022

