*-Collected as needed as a contingency outcome if no clinical weights. Also collected shortly after randomization following receipt of trial scale						
**-Outcome only collected among a subset of up to 250 participants						

5.5.2. Primary Outcomes: The co-primary endpoints for our pragmatic trial are changes in sleep-related quality of life and weight from baseline to 12 months. In secondary analyses, we will assess these outcomes at additional timepoints. Sleep-Related Quality of Life: The functional outcomes of sleep questionnaire (FOSQ) assesses multiple activities of daily living impacted by sleep disorders.⁶⁴ FOSQ addresses domains that are important to patients: activity level, vigilance, intimacy/sexual relationships, productivity, and social outcome. FOSQ has a high degree of internal reliability, strong criterion, and construct validity when compared against generic quality of life measures (e.g. SF-36) and sleep symptom inventories.⁶⁵ FOSQ is sensitive to changes in OSA treatment and is widely used in trials of OSA management. Weight Loss: Consistent with the pragmatic nature of this trial, we will prioritize clinically measured weights using methods shown to be feasible and valid when compared to research weights (Section 2.5.6). We will use participants' qualifying outpatient clinical weight in the four months prior to randomization as their baseline measure. To assess change, we will select the outpatient clinical weight that is closest to the 12-month post-randomization date within a 9–15-month post-randomization window, using a standard algorithm to remove implausible and erroneous values.^{29,62} Specifically, prior to unblinding, suspect weights will be flagged using criteria used in the D-ELITE trial.^{62,63} These criteria are the same as those used above for exclusion in the baseline period. Flagged weights will be reviewed in a blinded fashion by study staff for plausibility. Weights determined to be implausible or likely erroneous will be excluded from analysis. As in D-ELITE, we will prioritize primary care clinic weights, however we will substitute another outpatient clinic weight from within our collection window if a primary care weight is missing. To reduce missingness, we will ask patients to schedule a visit with their primary care clinic for a weight if they do not have a clinical weight documented by 12-months. We have found that patients can have vital signs checked and entered into the EMR without an encounter or co-pay. We used these methods in a prior VA weight loss trial and obtained follow-up clinic weights in 84% of participants (NCT 03260140).

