5.6 Data Analysis

5.6.1 Statistical Power for Primary Outcomes: We designed this pragmatic trial to achieve power of 0.9 for two primary outcomes at 12 months assuming 20% attrition. We target a two-sided type I alpha of 0.025 for each outcome to account for a Bonferroni correction. FOSQ: We plan to detect a meaningful and important difference for FOSQ between groups, 0.75 points,⁶⁵ and assume the known standard deviation for change in FOSQ of 2.5 points.^{65,79-82} We will retain power of 0.8, even with up to 39% attrition (Table 7). **Weight:** Participants in D-ELITE's self-directed arm lost 4.5 kg.⁴¹ Assuming weight loss in our comparator group is similar to average Veterans with OSA seeking weight loss, 1.2 kg,³³ we expect a 3.3 kg difference between groups.

This difference approximates a meaningful difference of 3% weight loss ([name] et al, JAMA, 2022, PMID: 36511927). Given known standard deviation in clinical weight change among Veterans' attempting weight loss of 6.9 kg/year,³³ we will have 0.99 power to detect this 3.3 kg difference in weight change with 20% attrition (Table 7). We will detect a 2.1 kg difference with power of 0.90. Similar to FOSQ, we retain power even with substantial attrition (Table 7).

Table 7. Power to detect differences in co-primary outcomes					
Change in Functional Outcomes of Sleep Questionnaire (FOSQ)					
Power	Alpha	SD (score)	Difference (score)	N	Attrition (%)
0.90	0.025	2.5	0.75	556	20
0.80	0.025	2.5	0.75	426	39
Change in Clinical Weight					
Power	Alpha	SD (kg)	Difference (kg)	N	Attrition (%)
0.99	0.025	6.9	3.3	556	20
0.90	0.025	6.9	3.3	220	68
0.80	0.025	6.9	3.3	170	76
0.90	0.025	6.9	2.1	556	20

5.6.2. Hypothesis Testing for Analyses of Trial Population: We will use intention to treat for analyses of primary and secondary outcomes of consented patients.

H1 (Primary Hypothesis): Lifestyle intervention will lead to greater weight loss and improvement in sleep-related quality of life at 12 months relative to usual care.

H2a (Secondary Hypothesis): Lifestyle intervention will lead to greater improvement in secondary outcomes measured at baseline and follow-up relative to usual care.

H2b (Secondary Hypothesis): Self-directed lifestyle intervention will lead to more favorable values for outcomes only collected at follow up (e.g., AHI, global ratings of change).

Using intention to treat, we will test primary (H1) hypothesis separately for each outcome (weight and FOSQ) using linear mixed effects model

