Methodology: We plan a hybrid type 1 pragmatic randomized controlled trial. We will proactively identify Veterans with OSA and obesity nationwide using data from the CDW (n=696), randomizing 1:1 to usual care plus the D-ELITE weight loss intervention or usual care alone. We will collect primary outcomes at 12-months, but we will also collect outcomes at 3- and 24-months to assess trends over time. For our implementation process evaluation, we will use quantitative and qualitative methods to assess barriers to implementation, including a comprehensive budget impact analysis.

2. Sample Size Rationale:

We designed this pragmatic trial to achieve power of 0.9 for two primary outcomes at 12 months assuming 20% attrition using a two-sample t-test of independent means (STATA version 16.1). We target a two-sided type I alpha of 0.025 for each outcome to account for a Bonferroni correction. FOSQ: We plan to detect an established meaningful and important difference for FOSQ between groups, 0.75 points, and assume the known standard deviation for change in FOSQ of 2.5 points. Weight: Participants in a prior version of the D-ELITE self-directed intervention lost 4.5 kg. Assuming weight loss in our comparator group is similar to average Veterans with OSA seeking weight loss, 1.2 kg, we expect a 3.3 kg difference between groups. This difference approximates a meaningful difference of 3% weight loss ([name] et. al., JAMA, 2022. PMID: 36511927). Given known standard deviation in clinical weight change among Veterans' attempting weight loss of 6.9 kg/year, we will have 0.99 power to detect this 3.3 kg

difference in weight change with 20% attrition (Table 1). We will detect a 2.1 kg difference with power of 0.90. Across both co-primary outcomes, we retain power of 0.8 even with 39% or more attrition (Table 1).

3. Description of how data will be collected:

We will enroll 696 Veterans nationwide. In CDW, we will identify Veterans with an eligible outpatient BMI and sleep study recorded in the past 6 months with associated diagnosis of OSA who are free from exclusionary conditions searchable in CDW.

- **Research invitation:** We will invite potentially eligible patients by mail and email, and will send an invitation letter, information statement, and an opt-in/out postcard and Qualtrics link.

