5. Plans for any interim analysis of the data:

We do not plan to perform any interim analyses for superiority, futility, or sample size re-estimation. The D-ELITE weight loss intervention is consistent with existing VA guideline-based care for obesity and obstructive sleep apnea. Our trial is therefore meant to promote recommended medical care, and we do not believe an interim analysis of the data is warranted.

6. Missing and Misclassified Data:

For our primary outcomes, we assume 20% attrition to retain power of 0.9. However, we expect to retain sufficient power, 0.8, even if we experience dropout of over 39% (Table 1). Our pragmatic trial prioritizes outcome collection from EMR, including JLV and CAPRI, to reduce participant burden and enhance generalizability. While we attempt to minimize missingness and misclassification through efforts to optimize follow up survey completion and validated approaches to decrease measurement error, we anticipate missing data. We originally considered complete case analyses, but ultimately chose an approach based on linear mixed models and maximum likelihood that is valid under the missing at random assumption. Linear mixed models impute missing outcome data implicitly within a hierarchical model, using

individuals' baseline, adjustment, and stratification values. Missing values of covariates will be imputed using the chained equations approach (e.g. MICE), using single imputation if missing rates are less than 5% and multiple imputation otherwise. We will carry out the recommended sensitivity analyses to the MAR assumption using methods based on pattern mixture models and imputation, by assuming a range of perturbations of imputed outcome values and assessing differences in model conclusions.

Table 1. Change in Functional Outcomes of Sleep Questionnaire (FOSQ)

Power	Alpha	SD (score)	Difference (score)	N	Attrition (%)
0.90	0.025	2.5	0.75	556	20
0.80	0.025	2.5	0.75	426	39
Change in Clinically Measured Weight					
Power	Alpha	SD (kg)	Difference (kg)	N	Attrition (%)
0.99	0.025	6.9	3.3	556	20
0.90	0.025	6.9	3.3	220	68
0.80	0.025	6.9	3.3	170	76
0.90	0.025	6.9	2.1	556	20

7. List and definitions of covariates to be included in models:

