As outlined in Section 9, our primary model will include a number of covariates. First, we will use each of the stratification variables as defined in Section 4, including BMI category, physiologic OSA severity on diagnostic sleep study, and sleep related impairment. We will also include adjustment variables "A" collected at baseline including patient's age, self-identified gender, self-identified race, Charlson comorbidity index and rurality. We will define gender and race based on self-identified characteristics collected in baseline surveys. We will use age documented in the electronic medical record at baseline, calculate Charlson comorbidity index using ICD-10 codes documented in VA electronic medical record in the year prior to randomization, and we will define rural residence by Rural-Urban Commuting Area (RUCA) codes, utilized by the VA Office of Rural Health to define rurality.

8. Methods for dealing with data transformations:

We do not anticipate the need to transform data elements prior to analysis.

9. Definitions of the analytic cohorts:

Intent to Treat: Primary analyses of treatment effects will be intent-to-treat, with participants analyzed in the groups to which they were randomized.

Hypothesis Testing:

H1 (Primary Hypothesis): Lifestyle intervention will lead to greater weight loss and improvement in sleep-related quality of life at 12 months, relative to usual care.

H2 a (Secondary Hypothesis): Lifestyle intervention will lead to greater improvement in secondary outcomes, measured at baseline and follow-up relative to usual care

H2b (Secondary Hypothesis): Self-directed lifestyle intervention will lead to more favorable values for outcomes only collected at follow up (e.g., AHI, global ratings of change).

Using intention to treat, we will test primary (H1) hypothesis separately for each outcome (weight and FOSQ) using linear mixed effects model

$$Y_{ij} = \beta_0 + \beta_1 T_j + \beta_2 X_i T_j + \beta_3 Q_i + \beta_4 A_i + u_i + \epsilon_{ij}$$

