- Clarified ambiguous language around review of adverse events. The prior version could have been interpreted as indicating the PI and another clinician would *both* review each adverse event. The current version has been corrected to describe that PI *or* another clinician will review each adverse event.
- In consultation with co-investigators and our local IRB of record, we are adding the development or exacerbation of eating disorders as an expected event given the high prevalence of these disorders within the Veteran population (Mitchell et. al. *Psychol Assess*, 2021, PMID: 34292003).

Version 3.1 7/31/2023

- Updates throughout changing secondary outcomes collection period for 24-months to 21-months. This change is made to allow uniform capture of longer-term outcomes in the funded timeframe of the study

Section 3. Description of how data will be collected:

- Clarified our methods around collection of weight data
- Updated our approach to participant remuneration, including additional payments made after primary outcome collection at 12 months.

Section 6. Missing and Misclassified Data and Section 9. Definitions of the analytic cohorts:

In consultation with our biostatisticians, we reconsidered our prior approach of ANCOVA with “complete case analysis”. Instead, we will pursue our primary and secondary hypotheses using linear mixed effects model because it is valid under the missing at random assumption. In addition, we will pursue multiple imputation using chained equations for missing covariate data if needed. (Note that outcomes have not yet been analyzed, and we are still in the process of collecting primary 12 month outcomes).

Version 3.2 4/15/2024

- Section 7. Updated to include definitions of the adjustment variables (age, gender, race, Charlson Score, rurality) which were previously included in Section 9 of our data analysis plan and published in our protocol paper ([name] et. al. *Contemp Clin Trials*. 2023 Dec;135:107378. doi: 10.1016/j.cct.2023.107378).

Version 3.3 06/12/2024

- Section 7. Updated this section to clarify that we will use all stratification variables, already defined in section 4 and listed in our protocol paper, in our primary analytic model.
- Section 9. Corrected formatting/font of the analytic model.

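### Bonferroni at 0.025 per outcome is valid, but Holm's procedure would add FOSQ power at the same 0.05 familywise error; separately, the dropout wording in SAP 6 goes beyond the FOSQ row of Table 1

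*SAP*

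**What the plan says.** SAP 2 and Protocol 5.6.1 set the same rule for the two co-primary outcomes: "We target a two-sided type I alpha of 0.025 for each outcome to account for a Bonferroni correction". Power comes from a two-sample t-test. The target is 0.9 at 20% attrition from 696 randomized 1:1. SAP 9 then says "we will test primary (H1) hypothesis separately for each outcome (weight and FOSQ) using linear mixed effects model". It does not repeat the alpha, and neither document mentions a step-down procedure.

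Three sentences describe how much attrition the design tolerates at power 0.8:
- Protocol 5.6.1, for FOSQ: "We will retain power of 0.8, even with up to 39% attrition".
- SAP 2: "Across both co-primary outcomes, we retain power of 0.8 even with 39% or more attrition (Table 1").
- SAP 6, for the primary outcomes and citing Table 1: "we expect to retain sufficient power, 0.8, even if we experience dropout of over 39" per cent.

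The FOSQ row for power 0.80 in SAP Table 1 (Protocol Table 7) is N = 426, with attrition given as 39%.

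**The concern.** FOSQ sets the sample size. The SAP's Summary of Edits for version 3.0 says that 696 is still needed for that outcome. At the expected 3.3 kg, weight is far overpowered. Under Bonferroni the 0.025 assigned to weight is spent once weight is tested. Under Holm it passes to FOSQ when weight is significant, with the same bound on familywise error and no extra patients. What is at stake is some avoidable chance of missing a real FOSQ effect.

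The second matter is one of wording. SAP 6 and Protocol 5.6.1 draw opposite conclusions from the same table row. One places the safe region above 39% and the other places it at or below 39%. A reader of SAP 6 could think that FOSQ power is secure at dropout levels the table does not cover.

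**Working it through.** **Inputs** (SAP 2, Table 1 and SAP 4): FOSQ difference 0.75, SD of change 2.5; weight difference 3.3 kg (also 2.1 kg), SD of change 6.9; two-sided alpha 0.025; 1:1 allocation; 696 randomized. The 1 kg and zero weight effects are added here to show sensitivity.

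**Step 1. Reproduce Table 1.** Two-sample t-test power from the noncentral t, with noncentrality difference / (SD × √(4/N)):

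| Outcome | N | Attrition, 1 − N/696 | Power stated | Power found |
|---|---|---|---|---|
| FOSQ 0.75 | 556 | 20.1% | 0.90 | 0.901 |
| FOSQ 0.75 | 426 | 38.8% | 0.80 | 0.801 |
| Weight 3.3 kg | 556 | 20.1% | 0.99 | 0.9996 |
| Weight 3.3 kg | 220 | 68.4% | 0.90 | 0.901 |
| Weight 3.3 kg | 170 | 75.6% | 0.80 | 0.803 |
| Weight 2.1 kg | 556 | 20.1% | 0.90 | 0.910 |

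All rows agree.

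**Step 2. Familywise error.** With both nulls true, either method makes an error only if at least one p-value is below 0.025. The rate is the same for both: at most 0.05, and 1 − 0.975² = 0.0494 if the outcomes are independent. With one null true, Holm tests that outcome at no more than 0.05. The bound is therefore 0.05 throughout, under any dependence.

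**Step 3. FOSQ power under Holm, t-test basis, N = 556.** FOSQ power is 0.9010 at alpha 0.025 and 0.9419 at alpha 0.05, a difference of 0.0408 before rounding. Taking the two tests as independent,

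Holm power = 0.9010 + 0.0408 × (weight power at 0.025).

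| Weight effect | Weight power | FOSQ power, Holm | Gain (points) |
|---|---|---|---|
| 3.3 kg | 0.9996 | 0.942 | 4.1 |
| 2.1 kg | 0.910 | 0.938 | 3.7 |
| 1 kg | 0.296 | 0.913 | 1.2 |
| none | 0.025 | 0.902 | 0.1 |

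At 3.3 kg the chance of missing the FOSQ effect falls from 9.9% to 5.8%. Simulation with endpoint correlations of 0, 0.3 and 0.5 leaves the 3.3 kg result unchanged and gives 0.939, 0.936 and 0.934 at 2.1 kg.

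**Step 4. Planned mixed model.** The model in SAP 9 has a common baseline mean and lets residual variances differ between baseline and 12 months. Let r be the baseline to 12-month correlation and k the ratio of the 12-month SD to the baseline SD. Ignoring the other covariates, the variance relative to a change-score analysis is k²(1 − r²)/(1 + k² − 2rk), which is (1 + r)/2 when k = 1. The documents give neither r nor k, so both are assumed. FOSQ power at 3.3 kg and N = 556, with k = 1:

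| r | Bonferroni | Holm | Gain (points) |
|---|---|---|---|
| 0.3 | 0.984 | 0.992 | 0.9 |
| 0.5 | 0.967 | 0.983 | 1.6 |
| 0.7 | 0.944 | 0.969 | 2.6 |
| 0.9 | 0.916 | 0.952 | 3.6 |

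For r from 0.3 to 0.9, the gain is 0.2 to 0.8 points at k = 0.8 and 1.9 to 4.1 points at k = 1.25.

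**Step 5. Dropout wording, t-test basis, alpha 0.025.** FOSQ power is 0.801 at 38.8% attrition, 0.7996 at 39.0%, 0.792 at 40% and 0.753 at 45%. Weight holds 0.80 to about 76% at 3.3 kg, and to just under 41% at 2.1 kg (0.801 at 40.5%, 0.798 at 41%). Under the mixed model with k = 1, FOSQ holds 0.80 to about 42% (r = 0.9), 48% (r = 0.7) or 54% (r = 0.5). At k = 1.25 and r = 0.8 the variance ratio is 1, so the limit falls back to the t-test figure.

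**The case against.** The sponsor can fairly reply that nothing is broken. One clear and valid rule is stated, and the target of 0.9 is met. A reader might infer that Bonferroni is a mistake here or that FOSQ is underpowered; the reproduced table shows neither.

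Nor is Holm free. At 3.3 kg weight is almost always significant, so FOSQ is in effect tested at 0.05. If weight falls and FOSQ does not change, the FOSQ false-positive rate doubles from 0.025 to 0.05. That case matters, because Protocol 2.1.3 describes the evidence that weight loss improves patient-centred outcomes as limited. Holm can also reject FOSQ while its 97.5% confidence interval includes zero, in up to about 4% of trials. Preferring the stricter rule is legitimate. These objections stand, and they make the change optional.

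Timing is the stronger objection. The protocol abstract says analysis has not begun, but that progress section was last logged as changed in version 2.8 (02/22/2023), "section to reflect that recruitment began 4/4/2022". The SAP's own statement is in its version 3.1 entry (7/31/2023): "Note that outcomes have not yet been analyzed, and we are still in the process of collecting primary 12 month outcomes". The current SAP is dated 06/12/2024 and the current protocol 03/04/2025. Protocol 5.5.2 says that "prior to unblinding, suspect weights will be flagged using criteria used in the D-ELITE trial", which shows an intention to stay blinded for that step but gives no date. A reader might infer that outcomes by arm have been seen; the documents do not say so. They also do not establish the opposite as of today.

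On dropout, the sponsor can say that the excess over Table 1 is small, that no decision depends on it because N is fixed and no interim analysis is planned, and that the mixed model may keep 0.80 beyond 39%. That is fair. But SAP 6 cites Table 1, which is a t-test calculation, and the SAP gives no power calculation for the mixed model.

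**Conclusion.** The point holds as an optional improvement plus a minor correction.

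On the SAP's own basis, with 20% attrition, Holm adds 4.1 points of FOSQ power at 3.3 kg and 3.7 at 2.1 kg. The gain shrinks to 1.2 points at 1 kg and 0.1 with no weight effect, and it is never negative. For the planned model, a reader might quote a narrow gain such as 1.6 to 3.6 points. That range needs equal variances and a correlation of 0.5 to 0.9, while SAP 9 lets the residual variances differ and no correlation is given. The supportable statement is about 0.9 to 3.6 points for correlation 0.3 to 0.9 with equal variances, and about 0.2 to 4 points if the SD ratio lies between 0.8 and 1.25.

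SAP 6 goes beyond the row it cites and conflicts with Protocol 5.6.1. It would be too strong to call the sentence false for the planned analysis: it may hold there, but no calculation in the documents shows it. SAP 2 is correct if read as 39% for FOSQ and more for weight, so it needs only clarification.

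**What to change.** **1. Testing rule (optional).** Proceed only if it can be documented that no one has seen outcomes by arm; otherwise keep Bonferroni. In SAP 2 and 9 and Protocol 5.6.1 and 5.6.2, write: *The two primary outcomes will be tested with Holm's procedure at an overall two-sided 0.05. The smaller p-value is compared with 0.025 and, if significant, the other with 0.05.* Leave N and the model unchanged. Report 97.5% confidence intervals and state that the decision follows the Holm comparison, since the two can disagree. The cost is wording, the higher FOSQ false-positive rate when only weight differs, and the need to justify a late change.

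**2. Dropout wording (in any case).** In SAP 6, replace the phrase claiming more than 39% with *up to about 39% for FOSQ (t-test basis, alpha 0.025)*. In SAP 2, state the limits by outcome: *about 39% for FOSQ and about 76% for weight at 3.3 kg (just under 41% at 2.1 kg)*. This changes no analysis and can be made at any time.

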which models for each patient i their measure for each outcome (FOSQ and weight separately), incorporating time of measurement T_j (0 or 12 months), treatment by time interaction $X_i T_j$, stratification variables Q_i , and adjustment variables A_i including age, gender, race, Charlson comorbidity index, and rurality. The model will include a random normal intercept u_i for each patient and a random normal error term ϵ_{ij} , all assumed independent. The variances of the ϵ_{ij} will be assumed different at baseline and 12 months. Here, β_0 is the average baseline FOSQ/weight among the control and treatment groups combined (assumed equal due to randomization), β_1 is the expected change in FOSQ/weight over time in the control group, and β_2 , the quantity of interest in hypothesis H1, is the expected difference in the change in FOSQ/weight over time between the treatment and control groups, or equivalently the expected difference between groups at 12 months. In secondary analyses, we will incorporate primary and secondary outcomes from each time point (baseline, 3, 12, and 21 months). We will use the same model to test secondary outcomes captured only at follow up, omitting baseline values.

Additional Analytic Subgroups: In addition to analyses of the entire sample using intent to treat, we will analyze primary and secondary outcomes according to model 1 and model 2 in the following groups:

- 1) Subgroups defined by each of the three pre-specified strata (see section 4).
- 2) Subgroups defined by gender.
- 3) Patients who are prescribed continuous positive airway pressure and use <4 hours per night in the 90 days before the outcome period.
- 4) The subgroup of patients who are prescribed continuous positive airway pressure and use ≥ 4 hours per night in the 90 days before the outcome period.

10. Adverse and Serious Adverse Event Monitoring:

To ensure unbiased determination across arms at 12- and 21-month follow-up, we will ask participants to complete a survey about potential adverse events (AE), serious adverse events (SAE) and unanticipated problems (UP) employing a body system-based assessment. We define SAEs as those resulting in hospitalization or death.

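### The primary model gives strata and adjusters one coefficient for both visits; if their link with FOSQ shifts by 12 months, the SE is slightly too wide and arm-by-stratum missingness can bias the estimate

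*SAP*

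**What the plan says.** SAP 9 gives the model as "Y_{ij} = \beta_0 + \beta_1 T_j + \beta_2 X_i T_j + \beta_3 Q_i + \beta_4 A_i + u_i + \epsilon_{ij", and Protocol 5.6.2 gives the same one. It has two visits ("incorporating time of measurement T_j (0 or 12 months"). Only treatment is crossed with time; Q and A each appear once, without a visit index.

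On the strata, SAP 7 says: "First, we will use each of the stratification variables as defined in Section 4". These are the BMI grouping, OSA severity and the sleep-impairment cut-off. It then adds the adjusters ("including age, gender, race, Charlson comorbidity index, and rurality"). It mentions no covariate-by-time term.

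The baseline mean is common to both arms: the intercept is the "average baseline FOSQ/weight among the control and treatment groups combined (assumed equal due to randomization". On the residuals, SAP 9 says: "The variances of the ϵ_{ij} will be assumed different at baseline and 12 months". With a random intercept and two visits this is in effect a free 2 x 2 covariance matrix.

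SAP 6 and Protocol 5.6.3 give the reason for a mixed model: validity under missing at random, with missing outcomes implicitly imputed from baseline, adjustment and stratification values.

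**The concern.** A single coefficient forces a covariate to shift the baseline and 12-month means equally. The sleep-impairment stratum is a PROMIS T-score cut at 60 taken at baseline (SAP 4). Patients split on a baseline symptom score will usually differ less on a related scale a year later, so its link with FOSQ is plausibly stronger at baseline. That is a judgement; the documents give no figure.

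If the link does weaken, two things follow. The misfit goes into the residual covariance and widens the FOSQ standard error. Also, validity under missing at random requires a correct mean model: if FOSQ is missing at rates that depend on both arm and stratum, a wrong stratum effect at 12 months can carry over into the treatment estimate.

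**Working it through.** **1. The plan's own figure.** Inputs from SAP 2 and Table 1: difference 0.75, SD of change 2.5, N = 556 (696 x 0.8 = 556.8). On alpha: "We target a two-sided type I alpha of 0.025 for each outcome to account for a Bonferroni correction".

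SE = 2.5 x sqrt(4/556) = 0.212. Power = Phi(0.75/0.212 - 2.241) = Phi(1.296) = 0.90. The exact two-sample t-test gives N = 556 for power 0.90 and 426 for 0.80, so the plan's figures reproduce.

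**2. Structure.** Subtracting the two visits in the SAP equation gives

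Y12 - Y0 = b1 + b2 X + (e12 - e0).

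Q and A cancel.

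**3. Effect on the standard error.** Assumed inputs: FOSQ SD 3 at both visits and correlation rho = 0.65. These imply a change SD of 3 x sqrt(2 - 1.30) = 2.51, in line with the plan. Take one standardised stratum variable with correlation r0 with baseline and r12 with 12-month FOSQ. In units of the SD:

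- The common coefficient fitted by maximum likelihood is g = (1 - rho)(r0 + r12) / [2(1 - rho) - (r12 - r0)^2].
- Residual moments: v0 = 1 + g^2 - 2 g r0; v12 = 1 + g^2 - 2 g r12; c = rho + g^2 - g(r0 + r12).
- Error variance, planned model: v12 - c^2/v0.
- Error variance, visit-specific effects: 1 - (rho^2 + r12^2 - 2 rho r0 r12)/(1 - r0^2).
- Error variance, no covariate: 1 - rho^2 = 0.5775.
- SE = 3 x sqrt(4/556 x error variance).

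For r0 = -0.60 and r12 = -0.35: g = 0.35 x (-0.95)/(0.70 - 0.0625) = -0.5216; v0 = 0.6461, v12 = 0.9069, c = 0.4265. The planned model gives 0.9069 - 0.1819/0.6461 = 0.6254. Visit-specific effects give 1 - (0.4225 + 0.1225 - 0.2730)/0.64 = 0.5750. The ratio is 1.088.

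| r0 / r12 | Planned | Visit-specific | Variance ratio | SE ratio | SE, planned vs visit-specific |
|---|---|---|---|---|---|
| equal | same | same | 1.000 | 1.000 | same |
| -0.50 / -0.40 | 0.5768 | 0.5700 | 1.012 | 1.006 | 0.193 vs 0.192 |
| -0.60 / -0.45 | 0.5878 | 0.5719 | 1.028 | 1.014 | 0.195 vs 0.192 |
| -0.60 / -0.35 | 0.6254 | 0.5750 | 1.088 | 1.043 | 0.201 vs 0.193 |

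Power at 0.75 points in the last row is Phi(0.75/0.2012 - 2.241) = 0.931 against Phi(0.75/0.1930 - 2.241) = 0.950. Compared with the model with no covariates, the planned model's variance is 8.3% higher in the last row, 1.8% higher at -0.60/-0.45 and 0.1% lower at -0.50/-0.40.

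A harsher stress test used a 50/50 stratum whose FOSQ gap shrinks from 3 points to 1, with SD 3. It gives SE 0.203 against 0.187 and power 0.928 against 0.962. The SE is still below the planning value of 0.212.

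**4. Simulated standard error.** N = 696, 20% of 12-month FOSQ missing equally in both arms, blocks of 4 within stratum, correlations -0.60/-0.35, 800 runs. The planned model's mean SE was 0.2007 against an empirical SD of 0.1936. With visit-specific effects the figures were 0.1919 and 0.1918. Monte Carlo error on an SD from 800 runs is about 1/sqrt(1600) = 2.5%, so the planned test is mildly conservative by an amount not pinned down closely. There was no bias.

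**5. Missingness that depends on arm and stratum.** Assumed pattern: 20% missing in both control strata; in the intervention arm, 15% in the low-impairment and 35% in the high-impairment stratum (25% overall if the strata are equal in size). Given arm and stratum this is missing at random.

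| r0 / r12 | Bias, planned model | Bias, visit-specific |
|---|---|---|
| -0.60 / -0.35 | -0.10 | -0.006 |
| -0.60 / -0.45 | -0.06 | -0.008 |

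On a true 0.75, -0.10 is 0.10/0.75 = 13%. In the first row the test rejected in 0.845 of runs against 0.946. The mechanism is that the high-impairment stratum improves more between visits; losing more of it from one arm lowers that arm's observed change, and a constant coefficient cannot restore it. The reverse pattern biases upward.

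**The case against.** The case for leaving the model alone has real force.

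- **Size is assumed.** Nothing in the documents fixes the FOSQ SD, its correlation over time or its correlation with PROMIS. With constant effects the penalty is nil, and in the two milder cases it is 1.4% or less of the SE. This stands.
- **Little precision is being lost.** In these cases visit-specific adjustment lowers error variance by only 0.4% to 1.3% compared with no covariates, because baseline FOSQ is already in the model. The 8.8% is mostly a penalty for misfit, not stratification benefit forgone. This stands.
- **One covariate carries the argument.** No such shift has been shown for the other strata, for A or for weight. This stands, and is why Q-by-time is the minimum.
- **Changing again has a price.** The primary model has already moved from ANCOVA to the mixed model during 12-month collection (edit summaries, Protocol v2.10 and SAP v3.1), and SAP v3.2 says the adjusters were published. This stands as a small pre-specification cost.

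Three stronger readings are tempting and are not supported. A reader might infer that the trial falls below its design power; with similar missingness across arms the SE stayed below 0.212 in every scenario tried. A reader might infer that the covariates are useless, or that SAP 6 is wrong to say they inform missing outcomes; because baseline is constrained equal across arms, they still contribute to the 12-month value given baseline. And a reader might infer that the planned estimate is biased as it stands; bias appeared only when missingness varied with arm and stratum together.

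That last condition is hypothetical but not far-fetched. FOSQ is a survey measure (Protocol Table 5), and Protocol 6.3.1, on adverse events, itself allows for survey response differing by arm.

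**Conclusion.** The structural point is certain: Q and A have time-constant effects and leave the modelled mean change. The consequence depends on whether those effects truly change between visits. Under SD 3, correlation 0.65 and N = 556, the FOSQ SE is 0% to 4% wider than with visit-specific effects, and the largest case still has power of about 0.93. With missingness similar across arms the estimate is unbiased, the error is conservative and the planned 0.90 holds.

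The more useful reason to act is robustness. Under one assumed arm-by-stratum missingness pattern the planned model was biased by about -0.10 on 0.75, against about -0.01 with visit-specific terms. Those terms therefore support the missing-at-random validity for which the SAP chose this model. This is a low-severity improvement, not a flaw that undermines the primary analysis.

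**What to change.** In SAP 9 and Protocol 5.6.2, add Q-by-time and A-by-time terms to the primary model, at minimum Q-by-time, so that each covariate has its own coefficient at 12 months. With two visits this corresponds to ANCOVA on baseline, strata and covariates, while keeping patients who lack a 12-month outcome. Make the change by a dated amendment before unblinded analysis. If that point has passed, keep the planned model as primary and report the extended one as a labelled sensitivity analysis.

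The cost is about ten more parameters on some 556 analysed patients and one more documented change to the primary model. When the stratum gap was set equal at both visits, simulation showed no loss of precision (SE 0.1851 without the interaction, 0.1850 with it).
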